**F. Inclusion / Exclusion Criteria**

**Inclusion criteria:** Patients who have non-emergent cesarean deliveries, gestational age between 32 weeks and 0 days and 36 weeks and 6 days determined per usual clinical parameters.

**Exclusion Criteria:** Fetal anomalies or death, neonates with blistering skin conditions, reversed end diastolic umbilical artery flow, placental abruption, chorioamnionitis, monochorionic multifetal pregnancies, inability to provide consent, provider perception that patient is in significant pain and provider perceived contraindications to delayed cord clamping.

Since this is a pilot trial, we will not establish early termination criteria. However, if the DSMB asks us to stop the trial due to concern for patient safety we will comply.

**G. Gender/Minority/Pediatric Inclusion for Research**

Since this study aims to optimize outcomes for newborn preterm neonates with an intervention that is performed at the time of delivery such a study cannot be completed without participation of neonates or their mothers. As mentioned, the risks to mothers

should not be increased because of this intervention as there are no additional interventions beyond standard of care delayed cord clamping that will be required of mothers. On the neonatal side, there is a risk for neonatal iatrogenic hyperthermia defined as temperature  $>37.5$  degrees Celsius; however, no clinically important adverse outcomes have been identified in previous studies.

This study involves viable neonates (gestational age  $\geq 32$  weeks) and pregnant women. The proposed interventions are aimed at neonatal resuscitation, as such they should not impact maternal wellbeing. The intervention will be completed in a sterile fashion similar to all the procedures of the cesarean delivery. The research is aimed at directly improving neonatal outcomes, and this particular intervention has been demonstrated to be safe if applied at a different time point in the neonatal resuscitation process. The informed consent process will include the risks and potential benefits associated with the proposed study. As expected, assent cannot be obtained from neonates. When obtaining consent from mothers younger than 18 years old, we will obtain consent from the patient and her parents, as she will be making decisions regarding her child's wellbeing immediately after birth and is considered empowered to do so under Oklahoma law. The overall risk level for pregnant patients is low as the procedures do not affect their wellbeing. The risk for neonates is also low because similar interventions have been investigated in the past at a different time point in the neonatal resuscitation process without evidence of significant adverse consequences.

#### **H. Recruitment and Enrollment**

Women who are admitted to the University of Oklahoma Children's Hospital Labor and Delivery or Antepartum unit will be screened by study personnel for eligibility. They will be approached about voluntary participation by trained study personnel. Research nurses are independent of the treatment team. Patients to be screened will be identified from the EMR by research nurses or by phone call from admitting physicians. If the patient is eligible the study will be introduced by research nurses independent of the treating/admitting physicians and they will be provided with an informed consent form. Interested participants will be consented either on the antepartum unit or the labor and delivery unit.

Last, it is impossible to recruit patients outside of the inpatient setting for a study investigating preterm delivery, as such deliveries are rarely predictable in the outpatient setting. There will only be one site for this study, the OU Children's Hospital labor and delivery and antepartum units. Patients who are imminently delivering, or in significant pain per the judgement of treating physician or nurse will not be approached to minimize the risk of coercion. Study personnel will administer an informed consent interview with each participant, which includes a verbal explanation of the study in lay terms.

Participants will also receive a written informed consent form. Potential participants are told that they need not participate in this research study, that the study may or may not benefit them directly, that they would be contributing toward a better understanding of treatments for preterm newborns, and that they may decline participation. The consent process also describes alternative options for the person considering research participation (including the right to decide not to participate in any research), privacy protections, potential circumstances involving loss of privacy, and what to do in case of adverse events. All potential participants are given adequate time to make a decision, have a chance to have their questions answered prior to making a decision, and are encouraged to include trusted relatives, friends, and/or other healthcare providers when making a decision. Once the informed consent has been signed, the participant is considered enrolled in the study. At this time, study-specific procedures may be

performed. Informed consent forms will be available in both English and Spanish, and if required hospital translator services will be used to assist in translations during the consent process. A patient's capacity to consent will be determined by her treating physician, if in their opinion they cannot consent to clinically relevant procedures they will not be approached for consent.

Enrollment will be stratified by gestational age with a goal recruitment of at least 44 pregnancies at 32-34 weeks and 6 days gestation and 20 pregnancies between 35-36 weeks gestation.

**I. Risks and Benefits**

This intervention has been previously evaluated at a different time point in the neonatal stabilization process in various studies. A previous study where infants were wrapped from the initiation of resuscitation until admission to the neonatal intensive care unit a 7% risk of hyperthermia with no associated adverse neonatal clinically important consequences. Hyperthermia in this population is defined as temperature >37.5 degrees C. The effect of a combination of warming mattresses and polyethylene wraps is mixed as one study notes a 28% risk of hyperthermia at admission to the NICU in neonates born at less than 31 weeks, while another did not identify any children with hyperthermia. Neither study reported adverse clinical consequences. Perlman and colleagues evaluated 3 observational studies for a total of 8985 patients showing no increase in the risk of hyperthermia. Certainly, we would expect a lower rate of hyperthermia, as the intervention will only be applied until the infant can be brought to the neonatal warmer for a total of 2-3 minutes, contrasted with a longer exposure in the above studies. Of note, none of the above studies have demonstrated an increased risk of adverse clinical outcomes in the setting of iatrogenic hyperthermia. As such, the risk level from the proposed study is likely very low. Similarly, since the study will involve extraction of identifiable data there is an extremely low risk of violating privacy and confidentiality as all staff involved are trained to follow HIPAA and the data will be stored on a secure server.

All study procedures will follow good clinical practice. Risks of adverse events will be reduced by the study personnel and the investigators regularly monitoring participants' progress, by oversight of the IRB, and the data safety monitoring board (DSMB). Patient participation may be stopped by the delivering physician if there is concern for intrauterine infection or placental abruption. In addition, the neonate will be evaluated by a physician or nurse practitioner trained in neonatal resuscitation during the intervention as is currently the standard of care. The intervention may be discontinued or halted from initiation if the neonatal health care provider deems that there is a blistering skin disease that makes the neonate unsuitable for participation. Immediate access to higher levels of care from staff neonatologists are available at University of Oklahoma Children's Hospital Labor and Delivery 24 hours a day with direct access available via the use of an internal paging system. Finally, both devices to be used during this study (neonatal wrap and warming mattress) will follow FDA labeling.

Participant confidentiality will be protected by our strict adherence to HIPAA guidelines. As specified in the informed consent process, it is not possible to ensure complete protection of a subject's identity. However, any breaches of good clinical practice in this regard would be taken extremely seriously, with appropriate reporting and regulatory actions. All patients will be assigned a study participation number, which will be used to track the patient and their neonate throughout the study. All patient related data will be

stored on secure University servers with access limited to only relevant research personnel and will be password protected (REDCap database). All study personnel are accredited by university-approved online Human Subjects in Research Safety Programs. The PIs will be responsible for steps to protect against risks, including but not limited to training in Protection of Human Subjects for all study personnel, security of database systems, locking of any areas containing medical records, and protection of vulnerable populations.

#### **J. Statistical Methods**

Since this intervention has not been studied previously and requires cohesion between pediatricians and obstetricians, we will plan on hosting in-person and virtual training for key study personnel. Currently, at OU we deliver approximately 250 neonates between 32 and 36 weeks gestation via cesarean each year. Assuming a 33% rate of enrollment, it would take us approximately 11 months to enroll our target sample size of 74 patients.

Two prior studies, one evaluating epidemiology and the other an intervention, demonstrated that 29% of neonates born in the late preterm period were hypothermic in the delivery room with a standard deviation of 8.8. With the proposed enrollment of 74 preterm infants that meet inclusion criteria, we would have approximately 80% power to detect a difference between the two groups of 20%. Since this intervention has not been evaluated previously and we are using indirect data from other institutions and other interventions, we are assuming a 10% increase in sample size (calculated at 68) to account for variations (total of 74). This is a pilot trial to generate the parameters needed to guide the development of the next-step full-scale multicenter trial. Thus, power calculations for the efficacy of the intervention were completed to ensure we did not need to start with a larger or smaller sample size, given the pilot nature of the project.

For this pilot trial, the baseline characteristics of patients assigned to the intervention and control groups will be estimated and compared as means, medians or proportions, as appropriate for the distribution of the data. Descriptive statistics (i.e., proportions, 95% confidence intervals, means, standard deviation, medians, and interquartile range) will be used to characterize the distribution of the primary and secondary outcome measures among the intervention and control groups. Using an intent-to-treat approach, the primary and secondary outcomes will be compared between treatment groups using Student's t-tests, Wilcoxon rank sum tests, chi-square tests or Fisher's exact tests, as appropriate for the variable distributions.

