#### **A. Specific Aims**

We *hypothesize* that neonates delivered preterm and wrapped with a sterile polyethylene wrap while being warmed with a standard neonatal transport warming mattress immediately after birth and awaiting delayed cord clamping will be less likely to be hypothermic at arrival to the neonatal warmer. Since this is not currently a method that is employed, we have insufficient preliminary data to determine a sufficient sample size needed for a randomized controlled trial. **The aim of this grant is to perform a pilot trial investigating the effect size of immediate neonatal warming and wrapping of preterm infants on neonatal temperature.** Our team is well positioned to address these questions as there is tremendous synergy between the maternal fetal medicine and neonatology groups at OU, and our large referral base for preterm deliveries—we accept 600 maternal transfers yearly.

We propose a pragmatic randomized pilot trial evaluating the effect size of this strategy employed for moderate and late preterm infants (32 weeks 0 days to 36 weeks 6 days) who are being delivered by non-emergent cesarean. We plan on enrolling 74 patients and allocating patients to the intervention and control groups 1:1 using a block randomization scheme stratified by gestational age. Patients and clinicians cannot be practically blinded to the interventions given the physical nature of the interventions; however, statisticians will be blinded to the group assignments. Primary outcome will be the difference in temperature of the neonate at time of arrival to the warmer for neonatal evaluation between groups. Secondary outcomes will include temperature at completion of resuscitation, need for NICU admission, temperature upon leaving the delivery room, temperature upon admission to the NICU (if required), hypoglycemia (less than 30mg/dL in the first 24 hours), highest bilirubin level, respiratory support in the form of intubation or continuous positive airway pressure, pulmonary hemorrhage, hyperthermia ( $>37.5$

degrees C), days in the NICU, and composite neonatal morbidity and mortality outcome of death or intraventricular hemorrhage (all grades), sepsis (determined by treating neonatologist). Data obtained from this pilot trial will be used to apply for a NIH K08 grant in order to perform an adequately powered multi-center randomized controlled trial in order to investigate the efficacy of this approach and associated outcomes.

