### Hypothermia and Neonatal outcomes

An important component of care in the first few minutes of life, especially in the preterm neonate is ensuring euthermia. Neonates have decreases in their body temperature of 0.2-1 degrees per minute after birth. Preterm neonates are at increased risk for hypothermia due to their increased body surface to weight ratios, thin skin and lower amounts of insulating subcutaneous fat, thus resulting in increased evaporative heat losses. Hypothermia results in increased metabolic and oxygen demands and impaired resuscitation. From an outcome perspective, hypothermic neonates are at an increased risk for respiratory distress, chronic lung disease, metabolic derangements such as hypoglycemia, intraventricular hemorrhage, and late onset sepsis. Even moderate hypothermia (<36 degrees C) has been linked to mortality. De Almeida et al noted that 44% of preterm neonates admitted to one of 12 university hospitals were hypothermic at 5 minutes of life, with 51% experiencing hypothermia at NICU admission. As such, various interventions have been studied during the golden hour and at the time of neonatal transport to the NICU. These include using polyethylene wraps and caps, warming mattresses, warmed humidified gases and maintaining delivery room temperatures at 24 degrees C. Though such interventions may result in hyperthermia (>37.5 degrees C), no correlation between iatrogenic hyperthermia and adverse neonatal outcomes has been demonstrated. However, strategies to avoid hypothermia reduce the need for respiratory support and lower the risk of pulmonary hemorrhage. Thus, beginning to prevent hypothermia during delayed cord clamping presents itself as an opportunity for improvement in outcomes.

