### **D. Research Design and Methods (What, When, How, Where)**

### Recruitment

The trial will be advertised and introduced to patients admitted to the OU Children's Hospital labor and delivery or antepartum units by research nurses. Interested participants will be consented. We are choosing to only include patients undergoing non-emergent cesarean in order to improve our ability to control parameters such as room temperature and labor-related clinical or subclinical maternal infection, which are known confounders. Further, we are limiting our investigation to fetuses 32-36 weeks gestation, since this population represents the largest preterm delivery population. Recruitment and randomization will be stratified by gestational age with an aim to enroll at least 44 pregnancies at 32- 34 weeks and 6 days and 20 pregnancies between 35- 36 weeks and 6 days. Last, it is impossible to recruit patients outside of the inpatient setting for a study investigating preterm delivery, as such deliveries are rarely predictable in the outpatient setting. There will only be one site for this study, the OU Children's Hospital labor and delivery and antepartum units.

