We will aim for an operating room temperature of 65-70 degrees F. The surgical technician will be provided with the necessary neonatal wraps and mattresses in a sterile fashion, and they will ensure these are available on the surgical field once the cesarean has begun. In the intervention group, the thermal mattress will be activated immediately prior to hysterotomy and placed on the sterile field with delivery of the infant directly onto the mattress. The infant will be dried, stimulated and bulb suctioned as deemed necessary per standard of care followed by wrapping. In the non- intervention group, the infant will be delivered onto the sterile field, dried and suctioned as deemed necessary per OU standard. Cord clamping will be delayed for 60 seconds in all infants under the supervision of both the obstetrician and the neonatal resuscitation team. If either team believes delayed cord clamping is no longer considered safe, as is our usual protocol, the cord will be clamped and cut and the baby will be handed off to the neonatology team. After the infant is handed to the neonatology team along with all group assignment specific materials (wrap and thermal mattress, if in the intervention group), neonatal temperature will be assessed immediately upon arrival to the resuscitation warmer using a digital thermometer placed in the axillary space. Infant temperature will be recorded at 1) arrival to the warmer, 2) after the neonatologist deems that in-room resuscitation is complete and 3) at admission to the Neonatal Intensive Care Unit (NICU), Mother Baby Unit (MBU) or Post-Anesthesia Care Unit (PACU) depending on the baby's needs; determined by the resuscitating physicians. These measurements will be recorded by research nurses in a data collection sheet. Further, the research nurse will record the time from delivery to the time it takes for the infant to arrive at the warmer. Upon arrival at the warmer, the mattress and wrap will be removed as neonatal evaluation takes place.

As immediate neonatal temperature is not generally discussed with patients unless there is an issue such as concern for infection, neonatal temperature will not be routinely discussed with all participants. Only if there is concern for neonatal infection or if there is hyperthermia (>37.5 degrees C) will the study results be discussed with the patient.

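### The 29% hypothermia rate behind the power check comes from late preterm data, while the trial enrols moderate and late preterm infants; power should be restated over a range of control rates with the scale of the 20% difference declared

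*Combined protocol and SAP*

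**What the plan says.** Section J (Statistical Methods) rests its power check on two prior studies that "demonstrated that 29% of neonates born in the late preterm period were hypothermic in the delivery room", "with a standard deviation of 8.8". From this it claims "approximately 80% power to detect a difference between the two groups of 20" per cent. It does not state alpha, sidedness, or whether the 20% is absolute or relative. The total comes from a "10% increase in sample size (calculated at 68) to account for variations (total of 74"). The same section concedes that the data are indirect, from other institutions and other interventions.

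The population to be enrolled is wider. Section A (Specific Aims) describes "moderate and late preterm infants (32 weeks 0 days to 36 weeks 6 days) who are being delivered by non-emergent cesarean". Section D (Recruitment) aims for "at least 44 pregnancies at 32- 34 weeks and 6 days" and 20 at 35 to 36w6d, and Section H repeats these goals. Randomization is stratified at the same gestational-age boundary.

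The protocol gives one other rate for the first minutes of life. Section B (Hypothermia and Neonatal outcomes) cites a report that "44% of preterm neonates admitted to one of 12 university hospitals were hypothermic at 5 minutes of life". The gestational range and cut-off behind that figure are not given.

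**The concern.** Section A names two groups, moderate and late preterm, and Section J takes its rate from one of them. On the recruitment goals, most participants fall in the younger stratum. Section B itself attributes the hypothermia risk of preterm infants to body proportions, thin skin and little insulating fat, so it is natural to ask whether the younger stratum runs a different rate. Section J makes no allowance for gestational mix, although gestational age is the stratification factor.

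What is at stake is the power statement and the pilot's usefulness as a source of parameters. Section J says that the calculation was done to confirm that the starting sample size was about right, and that the pilot exists to supply inputs for a multicentre trial. The control rate is one of those inputs. Judging the observed rate against a single late preterm figure, with no breakdown by stratum, could mislead whoever sizes the next trial.

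**Working it through.** **Inputs.** From the documents: planning rate 29%; difference 20%; total 74 at 1:1, so 37 per arm; stratum goals 44 and 20; alternative rate 44%. Assumed because not stated: two-sided alpha 0.05; 29% is the control-arm rate; the intervention lowers it; one infant per pregnancy; a binary primary outcome, as in Section E.

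**Step 1: the plan's own figure.** For two proportions with mean p̄ and difference Δ,

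n per arm = [1.96·√(2p̄(1−p̄)) + 0.8416·√(p₁(1−p₁) + p₂(1−p₂))]² / Δ².

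For 29% vs 9%, p̄ = 0.19 and the two roots are 0.5548 and 0.5365, so n = (1.0874 + 0.4515)² / 0.04 = 59.2. That is 60 per arm, or 120 in total, against the plan's 68. One-sided 0.05 gives 94. One-sided 0.10 gives exactly 68, but the plan does not state that level. A means formula treating 29 as a mean with SD 8.8 also comes close. A relative 20% difference is 0.20 × 29 = 5.8, so n = 2 × 8.8² × 2.8016² / 5.8² = 36.1, which is 37 per arm or 74 in total. This leaves no room for the 10% increase and treats a proportion as a continuous mean. The stated figure is therefore not reproduced on a conventional reading.

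**Step 2: stratum mix.** 44/74 = 59% in the younger stratum. The goals sum to 64, so up to 54/74 = 73% could be there. If the younger stratum runs at 44% and the rest stay at 29% (an illustration, not an estimate):

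(44 × 0.44 + 30 × 0.29) / 74 = (19.36 + 8.70) / 74 = 37.9%.

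**Step 3: power at 37 per arm.** I summed the two binomial distributions exactly and rejected when the uncorrected chi-square test gave |z| ≥ 1.96. The first comparison holds a 20-point drop. The second holds the risk ratio 9/29 = 0.310.

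| Control rate | 20-point drop to | Power | Total N for 80% (formula) | Ratio 9/29, drop to | Power |
|---|---|---|---|---|---|
| 29% | 9% | 0.61 | 120 | 9.0% | 0.61 |
| 35% | 15% | 0.52 | 146 | 10.9% | 0.72 |
| 37.9% (weighted) | 17.9% | 0.49 | 156 | 11.8% | 0.76 |
| 44% | 24% | 0.44 | 174 | 13.7% | 0.85 |

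Hand check with the normal approximation, power = Φ{[Δ√n − 1.96·√(2p̄(1−p̄))] / √(p₁(1−p₁) + p₂(1−p₂))}:

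- 29% vs 9%: (1.2166 − 1.0874) / 0.5365 = 0.241, so power is 0.595.
- 44% vs 24%: (1.2166 − 1.3130) / 0.6548 = −0.147, so power is 0.441.

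Both agree with the exact values to within 2 points.

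**Step 4: detectable difference.** The smallest absolute drop for which the same exact calculation reaches 80% power at 37 per arm is about 23 points from 29%, 27 points from 37.9% and 29 points from 44%.

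**The case against.** The strongest reply is that Section J already admits that its data are indirect and adds 10%, that Section A says there is too little information to size a full trial, and that the pilot's own results will guide the next one. Proportions with 95% confidence intervals by arm are planned, and gestational age is both a stratification factor and an assessed confounder. This limits the consequence: feasibility is not threatened and no extra patients are needed. It does not remove the point. The caveat concerns other institutions and interventions, not gestational mix; an increase from 68 to 74 would not cover even a 35% control rate with the 20-point drop (146 needed); and a rate by stratum is not promised.

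A second reply is that a higher control rate need not cost power. That is correct. Power falls only if the 20 points are absolute. With the ratio held, it rises.

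Stronger readings are tempting, and the documents do not support them:

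- **That 29% is probably too low.** The conditions, cut-off and timing behind it are not given. The 44% was measured at 5 minutes, whereas Section B puts arrival at the warmer at 2 to 3 minutes, when continuing heat loss would have produced less hypothermia. So 44% is not a floor.
- **That 29% applies to none of the younger stratum.** The documents do not define late preterm, and that stratum runs to 34w6d. Overlap cannot be excluded.
- **That the quoted cooling rate of 0.2 to 1 degree per minute puts nearly all controls below 36.5 C on arrival.** The same arithmetic at 5 minutes gives 37 − 5 × (0.2 to 1) = 36.0 to 32.0 C, so every infant would be below 36.5 C, yet the protocol reports 44% hypothermic then. It does not predict rates, and 36.5 C is not declared as the trial's cut-off.
- **That the planned room temperature shows the rate is wrong.** Section D says "We will aim for an operating room temperature of 65-70 degrees F", but the rooms behind the 29% are not described, so there is nothing to compare.

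**Conclusion.** The point holds as a mismatch of uncertain size and direction. The single planning rate is labelled late preterm, at least 59% of the planned sample is to come from below 35 weeks, and Section J makes no adjustment. The 44% figure gives reason to think that the control rate could be higher, and no more than that.

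With a 20-point absolute drop, moving from 29% to the weighted 38% costs about 12 points of power (61% to 49%), and applying 44% to everyone costs about 17 (61% to 44%). None of these reaches the stated 80% or so. With the 9/29 ratio held, power is about 76% at 38% and 85% at 44%. At 44% the answer therefore runs from 44% to 85% on a choice that the plan leaves open, which is the best argument for showing a range. All of this assumes two-sided 5% and a binary outcome.

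Two related defects are separate: the figure of 68 does not follow from 29% vs 9% at a conventional alpha, and Sections A and E name different primary outcomes. Curing either would not make the 29% describe the whole enrolled population.

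**What to change.** In Section J:

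1. Say that 29% comes from late preterm data and is applied to a wider gestational range.
2. State alpha, sidedness, and whether the 20% is absolute or relative.
3. Replace the single power figure with a small table for 74 participants giving power and detectable difference at control rates from about 29% to 44%, including a value weighted by the stratum goals.
4. Keep 74.
5. List the control-arm hypothermia rate by gestational-age stratum, with its confidence interval, among the parameters that the pilot will report.

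The cost is some wording, one table and one added line of reporting, with no extra patients. If the 20% is declared absolute, the stated power becomes less favourable. The stratum intervals will be wide: at the goals, about 22 and 10 control pregnancies (44/2 and 20/2).

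### The stated 80% power for a 20% difference with 74 infants is about 60% for the proportion hypothermic (29% vs 9%, two-sided 5%), and the calculation cannot be reproduced as written

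*Combined protocol and SAP*

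**What the plan says.** Section J takes its planning inputs from two earlier studies, reported as showing that "29% of neonates born in the late preterm period were hypothermic in the delivery room with a standard deviation of 8.8". From these it claims that with 74 infants "we would have approximately 80% power to detect a difference between the two groups of 20" per cent. On how the total was reached it says "we are assuming a 10% increase in sample size (calculated at 68) to account for variations (total of 74"). It gives the calculation a purpose: "power calculations for the efficacy of the intervention were completed to ensure we did not need to start with a larger or smaller" sample size. The same section describes the study's role: "This is a pilot trial to generate the parameters needed to guide the development of the next-step full-scale multicenter trial".

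For analysis, section J lists Student's t-tests along with "Wilcoxon rank sum tests, chi-square tests or Fisher's exact tests, as appropriate for the variable distributions". Allocation is 1:1 (section D, Protocol), so the arms have 37 infants each, or 34 before the increase.

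The outcome that the power refers to is not settled. The power paragraph is worded for a proportion, and section E (Chart Review) makes the proportion of hypothermic newborns primary. Section A (Specific Aims) differs: "Primary outcome will be the difference in temperature of the neonate at time of arrival to the warmer". Section A also concedes that "we have insufficient preliminary data to determine a sufficient sample size needed for a randomized controlled trial".

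**The concern.** A drop from 29% to 9% is large, but 37 per arm is small for a binary outcome, and 80% power looks too high at any usual significance level. A standard deviation of 8.8 has no evident meaning for a yes/no outcome at 29%.

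If the proportion is primary, a reader would take the risk of missing a true fall from 29% to 9% to be 20%. The calculation is also the plan's stated reason for leaving the sample size as it is, and the team planning the next trial would inherit a figure that it cannot rebuild.

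**Working it through.** **Inputs from section J:** control rate 29%; difference 20%; SD 8.8; N = 68, raised to 74. **Assumptions, because the text does not state them:** alpha and sidedness as labelled below, and 20% read as absolute (29% vs 9%) or relative (0.80 × 29% = 23.2%) as labelled.

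**1. Reproducing the plan's figure.** Two routes match part of the text.

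*Route (a): two proportions, absolute 20 points.* The pooled formula is n per arm = [(z_α·A + z_β·B) / Δ]², with
- A = √(2 × 0.19 × 0.81) = 0.5548
- B = √(0.29 × 0.71 + 0.09 × 0.91) = √0.2878 = 0.5365
- Δ = 0.20 and z_β = 0.8416

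At one-sided 10% (z_α = 1.2816) this gives n = 33.8, so 34 per arm, or 68 in total. Power is 80.2% at 68 and 82.7% at 74. This returns the calculated 68, but the significance level is stated nowhere and the 8.8 is not used.

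*Route (b): two means, relative 20%.* The difference is 0.20 × 29 = 5.8 and the SD is 8.8, so d = 5.8 / 8.8 = 0.659. At two-sided 5%:

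| Difference | N | Power, t-test | Power, normal |
|---|---|---|---|
| 5.8 | 74 | 79.9% | 80.9% |
| 5.8 | 68 | 76.4% | 77.6% |
| 6 (5.8 rounded up, an assumption) | 68 | 79.1% | 80.3% |

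This uses the 8.8 and matches 80% at 74, but it treats a percentage as a measured mean. A yes/no outcome at 29% has a per-infant SD of √(0.29 × 0.71) = 0.454, or about 45 points. With that SD, d = 5.8 / 45.4 = 0.128 and power at 37 per arm is 8%. Nor is 29 a plausible mean temperature in °C, so the route does not serve the outcome in section A either. If 20 were an absolute difference with SD 8.8, 5 per arm would be enough.

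The two routes need opposite readings of the 20%, and the plan does not say which was used.

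**2. Power for the proportion hypothermic.** Power = Φ[(Δ√n − z_α·A) / B]. At n = 37, Δ√n = 0.20 × 6.083 = 1.2166.
- Two-sided 5%: (1.2166 − 1.960 × 0.5548) / 0.5365 = 0.241, so power is 59.5%.
- One-sided 5%: (1.2166 − 1.645 × 0.5548) / 0.5365 = 0.567, so power is 71.5%.

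By test, 29% vs 9%, 37 per arm:

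| Level | Pooled normal | Exact chi-square | Fisher |
|---|---|---|---|
| Two-sided 5% | 59.5% | 61.4% | 50.6% |
| One-sided 5% | 71.5% | 72.6% | 62.6% |

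At 34 per arm, two-sided 5%, the pooled normal value is 55.8%.

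**3. What 80% power would take at two-sided 5%.**
- For 29% vs 9%, the formula gives n = 59.2; 59 per arm gives 79.9% and 60 per arm gives 80.5%.
- With 37 per arm, 80% is reached at a rate of about 4.9% (24 points) by the pooled normal formula, about 5.7% (23 points) by exact chi-square, and about 4% (25 points) by Fisher.

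**4. If the 20% is relative (29% vs 23.2%), two-sided 5%.** Power at 37 per arm is 8.2%; 80% would need about 899 per arm.

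**5. If mean temperature is primary.** A two-sided 5% t-test with 37 per arm has 80% power for a difference of 0.66 SD. The plan gives no SD in °C with which to convert this.

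**The case against.** The strongest reply is that 60% depends on choices the plan does not make: the proportion as endpoint, an absolute difference, and two-sided 5%. The hypothesis in section A is directional, and at one-sided 10% the two-proportion formula returns exactly 68, with 83% power at 74. No stated alpha contradicts that. On this view the supported defect is that the calculation cannot be verified, not that it is wrong.

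Part of this stands: the shortfall is conditional and should be reported with its conditions. But one-sided 10% is a lenient level that a reader would not assume without being told, and it leaves the plan's own SD unused. At one-sided 5% the power is still only 71%.

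A second reply is that this is a declared pilot. Section A admits that the preliminary data are insufficient and defers efficacy to a larger trial, section J calls its inputs indirect, and no interim efficacy or futility analysis is planned. The next trial would be planned mainly from the observed rates and SDs. This limits the consequence and is a good reason not to change N. It does not remove the problem, because section J makes an efficacy power claim and uses it to support the sample size.

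A third point is that the 80% threshold shifts slightly with the test (23 to 25 points). That is correct, and any replacement sentence should name its method.

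**Conclusion.** The concern holds. For the proportion hypothermic, 74 infants do not give about 80% power for a 20% difference at either 5% level. For 29% vs 9%, power is about 60% at two-sided 5% (51% with Fisher) and about 71% at one-sided 5%; for a relative 20% it is about 8% at two-sided 5%. At two-sided 5% the chance of missing a true fall from 29% to 9% is therefore about 40%, not 20%. These figures assume 37 per arm and the labelled alpha and scale, none of which the available text states for this calculation. The two routes that reach 80% rest on an undeclared level or on a model that does not fit a yes/no outcome. This should be fixed, but it does not threaten the pilot's conduct, and the plan sets no go/no-go rule that depends on it.

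**What to change.** Keep N = 74 and rewrite the power paragraph in section J:

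- Name one primary outcome, and make sections A and E agree.
- State alpha, sidedness, the test, and whether the 20% is absolute or relative.
- Define the 8.8 (variable, unit, source) or remove it.
- Say which formula gave 68. Also, 68 × 1.10 = 74.8, which rounds up to 75, so the step to 74 needs a word.

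If the proportion hypothermic is primary, the sentence could read:

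> With 37 infants per arm at two-sided 5%, power for 29% vs 9% is about 60% (pooled normal approximation) or 51% (Fisher's exact test); 80% power is available only for a drop of about 24 points, to about 5% (pooled normal), or about 25 points, to about 4% (Fisher).

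If mean arrival temperature is primary:

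> With 37 infants per arm, a two-sided 5% t-test has 80% power for a difference of 0.66 SD.

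The second version needs an SD in °C and its source.

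Since the stated aim is to estimate an effect size, the team could instead justify 74 by precision. At 29% vs 9% the approximate 95% confidence interval for the difference has a half-width of 1.96 × √(0.2878 / 37) = 0.173, or about 17 points.

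The cost is protocol wording and a less favourable stated power. No extra patients are needed and conduct does not change.
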